10.4 Subgroup analysis

Planned pre-determined analyses, where numbers are sufficient, of patient groups with:

- Underlying bone marrow failure (defined as a white cell count <1.0 x 10⁹/L with an explanatory underlying diagnosis, e.g. haematological malignancy, receiving chemotherapy)
- Underlying liver disease (defined as acute hepatic failure as primary reason for ICU admission or severe chronic liver disease biopsy proven cirrhosis, portal hypertension or hepatic encephalopathy)
- Sepsis (defined according to Sepsis-3 criteria³⁹)

10.5 Interim analysis

There will be three interim analyses following the recruitment and follow-up to 90 days of 830, 1340 and 1850 patients. Interim analyses will include preliminary modelling of the thresholdsurvival curve to inform adaptation of the allocation ratio based on the probabilities that each modelled threshold has the highest survival percentage. Up to two outer thresholds (potentially at the same end of the spectrum) will be dropped if their posterior probability of having the highest survival percentage of 5%. Allowing for recruitment during the 90-day follow-up, the adapted randomisation ratios are anticipated to take effect after the recruitment of 1020, 1530 and 2040 patients.

10.6 Stopping rules

There will be no formal statistical rules for stopping for efficacy or futility, but the outer thresholds may be discontinued following planned interim analysis. However, the trial could be stopped if the DMEC raises concerns about harms.

10.7 Health economic evaluation

Within-trial (1 year) and modelled cost-effectiveness analyses (CEAs) will be undertaken. The CEAs will take a healthcare perspective, capturing resource use associated with delivering the intervention, hospital, and ICU length of stay (weighted by number of organ supports required), and the use of personal health services. The use of hospital outpatient visits and community services following discharge from the index admission will be collected via a health service questionnaire sent to patients at 90 days and 1-year post-randomisation and via linkage to the Medicare Benefits Schedule (MBS) and Pharmaceutical Benefits Schedule (PBS) datasets. At the same time, patients will be asked to complete the EQ-5D-5L questionnaire to capture health-related QoL (HRQoL). Survival status at 90 days and 1 year following randomisation will be obtained via participating sites and/or data linkage with the Australian and New Zealand Intensive Care Society (ANZICS) Adult Patient Database (APD).

Quality-adjusted life-years (QALYs) at 90 days and 1-year post-randomisation will be calculated by valuing each patient's survival time by their HRQoL according to the area under the curve approach. Unit costs for included resources will be obtained from national sources, and we will use bivariate regression models to allow for correlation between costs and QALYs, adjusting for the same baseline covariates as the clinical analysis. We will estimate cost-effectiveness for the same subgroups as for the clinical analysis and to inform the possibility of recommending different thresholds for platelet transfusion according to patient subgroup.

As the trial has more than two arms the CEAs will be summarised by a net monetary benefit (NMB) threshold-response curve over the time horizon, assuming a \$50,000/QALY willingness-to-pay threshold. We will use long-term ICU survival data to extrapolate the results of the 1-year within-trial CEA to a lifetime time horizon for the modelled CEA. We will perform probabilistic sensitivity analysis by bootstrapping our sample of patients with replacement stratified by treatment arm to characterise the uncertainty in the NMB.

11 Ethics

This study is to be performed in accordance with the ethical principles of the Declaration of Helsinki (June 1964 and amended 1975, 1983, 1989, 1996, 2000, 2008 and Note of Clarification 2002 and 2004), ICH GCP Notes for Guidance on Good Clinical Practice (CPMP/ICH/135/95) E6 R2, NHMRC National Statement on Ethical Conduct in Research Involving Humans (2023)⁴⁰.

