10.1 Sample size

Sample size was estimated from simulations across 7 hypothesised threshold-response curves for the 90-day mortality primary outcome. These simulations are available in the simulations appendix at https://www.icnarc.org/Our-Research/Studies/Current-Studies/T4P/About. A sample size of 2400 resulted in power of at least 92% across the different scenarios to recommend an optimum threshold with a true mortality within 2% (in absolute value) of the optimum mortality value (Table 2, simulation appendix). The sample size was increased to 2550 patients to allow for 6% refusal/withdrawal of consent post-randomisation (as in the "65" Trial³⁶).

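### The patient-level bootstrap named in section 10.7 cannot carry extrapolation uncertainty, so intervals around the lifetime net monetary benefit curve will be too narrow

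*Protocol*

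**What the plan says.** Protocol section 10.7 sets out two kinds of economic analysis: "Within-trial (1 year) and modelled cost-effectiveness analyses (CEAs) will be undertaken". The lifetime one is built as follows: "We will use long-term ICU survival data to extrapolate the results of the 1-year within-trial CEA to a lifetime time horizon for the modelled CEA". Both are reported in the same form: "the CEAs will be summarised by a net monetary benefit (NMB) threshold-response curve over the time horizon", valued at $50,000 per QALY.

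The sentence directly after the lifetime extrapolation gives the probabilistic sensitivity analysis: "bootstrapping our sample of patients with replacement stratified by treatment arm to characterise the uncertainty in the NMB". Section 10.7 names no other method for uncertainty in the NMB. It does not confine the bootstrap to the 90-day or one-year horizon, and it does not say whether one extrapolation serves all arms or each arm has its own.

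**The concern.** A bootstrap of trial patients reproduces sampling error in what those patients contribute: survival, costs and QALYs within follow-up. A lifetime model also needs survival, utility and cost beyond follow-up. Any such input that is not re-estimated from the resampled patients takes the same value in every replicate, so its uncertainty never reaches the result. A probabilistic sensitivity analysis of a model is meant to propagate exactly that uncertainty.

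At stake is the width of the intervals around the lifetime NMB curve, which section 10.7 makes the summary of the modelled analysis. A reader would take them as the full uncertainty about lifetime value at each threshold.

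**Working it through.** The protocol gives no figure for lifetime uncertainty, so there is none to reproduce. The calculation below is an illustration.

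**Inputs from the protocol**
- Value of a QALY: $50,000 (10.7).
- Five arms and 2,550 patients, so 2,550/5 = 510 per arm if equal. The total reproduces: 2,400/0.94 = 2,553, against 2,550 (10.1).
- Australian cohort of 500, described as large enough for an Australian economic evaluation (10.2), so 500/5 = 100 per arm.

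**Assumptions not in the protocol**
- One-year survival p = 0.60.
- Mean remaining QALYs per one-year survivor m = 6, with SD s among survivors of 0 or 4.
- CV of the extrapolated mean: 5%, 10% or 20%.
- Costs ignored.

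**Level of lifetime NMB at one threshold**

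Sampling SE = 50,000 × sqrt{[p(1−p)m² + p·s²]/n}
- n = 510, s = 0: 50,000 × sqrt(8.64/510) = $6,508
- n = 510, s = 4: 50,000 × sqrt(18.24/510) = $9,456
- n = 100, s = 0: 50,000 × sqrt(8.64/100) = $14,697
- n = 100, s = 4: 50,000 × sqrt(18.24/100) = $21,354

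Extrapolation SE = 50,000 × p × m × CV = $9,000, $18,000 and $36,000 at CV 5%, 10% and 20%.

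Understatement factor = sqrt[1 + (extrapolation SE / sampling SE)²]

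| Patients per arm | Survivor SD | CV 5% | CV 10% | CV 20% |
|---|---|---|---|---|
| 510 | 0 | 1.7 | 2.9 | 5.6 |
| 510 | 4 | 1.4 | 2.2 | 3.9 |
| 100 | 0 | 1.2 | 1.6 | 2.6 |
| 100 | 4 | 1.1 | 1.3 | 2.0 |

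In the top row the combined SE is $19,140 at CV 10% and $36,583 at CV 20%, against $6,508 from the bootstrap alone. A simulation with 480 per arm (2,400/5) and s = 0 gave factors of about 1.7, 2.9 and 5.5. In that least favourable case a nominal 95% interval for the level covers about 76%, 51% and 28%.

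**Difference between two thresholds, one shared extrapolation** (510 per arm, s = 0)

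SE of the survival difference = sqrt(2 × 0.24/510) = 0.0307. To first order, the factor for a true difference d is sqrt[1 + (d·CV/0.0307)²].
- d = 0.02, CV 10%: sqrt(1 + 0.0042) = 1.002
- d = 0.06, CV 20%: sqrt(1 + 0.153) = 1.07

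Keeping the product term (adding CV² under the root) gives 1.007 and 1.09, so the increase stays below 10%.

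The sign of the difference does not move. With a common positive m and no costs, the increment is d × m × 50,000 and its sign is the sign of d. The probability that it is positive is Φ(0.02/0.0307) = 0.74 at 2 points and Φ(0.06/0.0307) = 0.97 at 6 points, whatever the CV.

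**Difference between two thresholds, arm-specific extrapolation**

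With independent draws per arm (480 per arm, s = 0, d = 2 points), the simulation gave an SD larger by a factor of about 1.7, 2.9 and 5.6 at CV 5%, 10% and 20%.

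**The case against.** The strongest reply has four parts.

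- **The decision rests on contrasts, not levels.** The third objective in 7.3 compares the optimum threshold with usual practice, and the listed economic outcomes in 7.5 and 7.6 stop at 90 days and one year. A shared extrapolation largely cancels in a contrast. This stands, and it limits the point to a secondary analysis.
- **A large factor needs favourable assumptions.** It requires every survivor to have the same remaining QALYs, 510 patients per arm, and a CV of 10-20% that the documents do not supply. This also stands, which is why the range starts at 1.1. Two features are not modelled: adaptive allocation (10.5) will make arms unequal, and a fitted curve pools information across arms, which lowers the sampling error at a given threshold.
- **The section does not say that the bootstrap is the only method or that the survival data come wholly from outside the trial.** Section 7.6 lists survival over the longest follow-up obtainable, so part of the extrapolation could rest on trial patients. This is fair. The point therefore covers only inputs that are not re-estimated from the resampled patients.
- **Model distributions belong in a statistical or health economics plan.** Details do, but this does not dispose of the point. The protocol itself names a method and its purpose, straight after introducing the lifetime model, and for that horizon the named method does not serve the purpose.

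A reader might go further and infer that the probability of a threshold being cost-effective is overstated, or that the choice of threshold is unsafe. The documents do not support that. Under a shared extrapolation without costs the probability is unchanged. Differences in within-trial cost could shift it, but the protocol gives no figures from which to claim so.

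**Conclusion.** The point holds for the modelled lifetime analysis only, and it is minor. As written, the stated method gives intervals around the lifetime NMB curve that are too narrow. The factor is about 1.1 to 5.6 for the level at one threshold, and both ends depend on assumptions that the protocol does not supply. It would be wrong to state as fact that the intervals are several times too narrow.

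Differences between thresholds are barely affected if the extrapolation is shared. They are understated as well if it is arm-specific, and the protocol does not say which applies. The bootstrap is suitable in kind for the 90-day and one-year analyses, and no listed outcome is affected.

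**What to change.** In section 10.7, keep the stratified patient bootstrap for the 90-day and one-year within-trial analyses. For the modelled lifetime analysis, add that each bootstrap replicate also draws the long-term survival, utility and cost parameters from their distributions, with common draws across thresholds wherever the extrapolation is shared. Report both the lifetime NMB curve and the increments from the combined replicates, and state whether the extrapolation is shared or arm-specific.

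The cost is a sentence or two of text, a little more health-economic programming, and wider lifetime intervals. Sample size, data collection and trial conduct do not change.

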11.1 Ethics committee & research governance approval

The Australian coordinating centre will submit this protocol and any other relevant study documentation to the HREC. Sites will submit to their research governance office for local authorisation. It is the site PI's responsibility to ensure that all conditions for approval of the study are met and that amendments to the protocol or serious adverse events are also reported to the HREC (or equivalent) as required by that committee. The inclusion in the trial of adults with incapacity to consent will be governed in accordance with the legal jurisdiction of each participating site.

11.2 Ethical considerations of the study

The ethical considerations of this study are:

- The risk/benefit ratio of the study treatment
- Data protection and confidentiality of participant data
- The enrolment of participants who are unable to consent for themselves

11.2.1 The risk/benefit ratio of the trial's comparison of standard care treatment arms

The range of platelet counts over which platelet transfusions are given to critically ill patients prior to a low bleeding risk invasive procedure is wide, with the majority occurring in patients with a platelet count in the range < $10-50 \times 10^9/L^{6,8,33-35}$. The five transfusion threshold arms of this trial encompass this range of usual care, and this trial is therefore comparing the effectiveness of these five strategies accepted by substantial numbers of medical practitioners specialising in the area of practice concerned. Participants in all arms of the trial will therefore be receiving treatment within the bounds of accepted standard clinical practice with no components of care being new or experimental. The treating clinician is expected to have equipoise about which of the five treatment strategies to employ in order to enrol a participant into the trial. Regardless of the treatment arm, and, because the trial is unblinded, the treating doctor retains ultimate control over whether the patient receives a platelet transfusion or not. The treating doctor may deviate from the treatment protocol if deemed to be in the interest of the participant (with the reasons for this documented in the CRF). Thus, participants in the trial are considered to be at no greater risk than if they were receiving treatment outside the trial. Thus, the risk/benefit ratio of the trial where both trial arms are encompassed by the range of usual care and is accepted as such by medical practitioners specialising in the area of emergency medicine and intensive care in Australia and New Zealand confers no greater clinical risk than receiving routine treatment.

11.2.2 Data protection and confidentiality of participant data

All investigators and research staff will comply with the legislative requirements of their jurisdiction with regard to the collection, storage, processing and disclosure of personal information. Confidentiality of all participant data will be maintained by the use of unique identifiers, password protected electronic databases, secure storage of records and precautions to control access to authorised personnel only. All records will be kept in compliance with local ethical and research governance policies.

Participants will be randomised via a secure database and allocated a unique study number. The site research coordinator will compile an enrolment log which contains identifying information. Subsequent data will be identified by the unique study number only. The enrolment log and study data will be kept separately. Follow-up details of the participant and their person responsible (if the participant has not regained adequate capacity) will be collected for the 90 day and 1 year outcome assessment conducted via telephone including name, address and contact telephone numbers/email. These contact details will be kept confidentially at the site in a locked filing cabinet in the site research office and will not be accessible outside the research team of the recruiting hospital.

11.2.3 The enrolment of participants who are unable to consent for themselves

Who may give consent for a patient to take part in medical research will vary between legal jurisdictions according to their local legislation. Each site's PI is responsible for ensuring that the relevant local legal requirements are followed. The term used to describe the person who may give

consent for a patient to take part in medical research will also vary between jurisdictions. For the purposes of this protocol, the descriptor 'person responsible' describes the person who is legally allowed to give consent for the participant.

All interaction between research staff and participants and their relatives will take into consideration the stress or emotional factors associated with critical illness and ensure that the dependency of potential participants and their relatives on medical personnel providing treatment does not compromise the freedom of a decision to participate. Consenting to participation will be voluntary and participants or their PR will be free to withdraw from participation at any time without giving reasons.

11.2.3.1 Urgent need for procedure and trial inclusion unable to be separated

Due to the critical nature of participant condition, the invasive procedure needs to occur rapidly often under emergency conditions and is part of being able to deliver life-saving care. Therefore, the study treatment arms, all which encompass standard care for patients with platelet counts of $< 50 \times 10^9$ /L requiring invasive procedures, cannot be separated from lifesaving care.

11.2.3.2 Unable to obtain patient or person responsible consent prior to enrolment

Time-critical invasive procedures often occur in the first hours of a critical care unit admission. Analysis of the Post-Intensive Care Risk-adjusted Alerting and Monitoring dataset⁴¹ and the DRIVE (Desmopressin for procedures or Radiological InterVEntions) study dataset⁴² shows that a large proportion of platelet transfusions occur on the first day in a critical care unit when critically ill patients commonly lack capacity. Both datasets also show platelet transfusion commonly occurs out-of-hours. The trial cannot delay these interventions but excluding these patients would impact upon the scientific validity. The emergency clinical situation and time-critical nature of invasive procedures can also cause profound distress for relatives, raising ethical concerns both about the burden of trying to understand the trial and the ability of the person responsible to provide an opinion about trial participation during a time of great distress, as recognised in section 4.4.11 of the National Statement⁴⁰. In addition, delaying the clinical procedure while an urgent opinion from a person responsible is sought would not represent usual clinical practice and might delay essential treatment. For these reasons, attempts to obtain prior consent from a person responsible when the patient lacks capacity to consent, is inappropriate.

11.3 Waiver of consent for enrolment and consent for follow up

In view of the above, we will seek approval for enrolment without consent where this is consistent with local jurisdictional requirements and legislation. This approach is in line with the principles in paragraph 4.4.13 of the National Statement and is justified on the basis that the trial is comparing the effectiveness of five accepted treatment strategies and trial participation confers no greater clinical risk than receiving routine treatment, as detailed in protocol section 11.3. As reasonably practicable following recruitment, the PR and/or the participant will be informed of the participant's inclusion in the trial and consent for follow up sought.

Dependent on local jurisdictional requirements and legislation, consent for follow up at 90 days and 12 months will employ either one of the following two approaches:

- Opt-out
- Consent to continue

11.3.1 Consent for follow up using opt-out approach

Subject to local HREC approval and where opt-out approach to consent is consistent with local jurisdictional requirements and legislation, we will request an opt-out approach for follow-up at 90 days and 12 months following trial enrolment. We believe the conditions for this opt-out approach, as described in the National Statement 2.3.5 and 2.3.6⁴⁰ have been met in the T4P trial. Refer to Appendix 2 for the National Statement 2.3.6 opt-out approach criteria and the trial's specific meeting of these conditions. In our experience with trials in critically ill patients when approval for enrolment without prior consent has been granted, consumer representative advice is that participants and PRs often find it confusing to provide written consent for data when the research treatment procedures have already taken place and they frequently perceive that more research specific interventional procedures are required.

Where an opt-out approach is approved, the site PI, or their nominated delegate, will provide a plain language brochure to the participant and/or PR at the earliest opportunity. The brochure will explain the trial and the procedure to decline or opt-out from follow-up. Additional to this written information, the site PI, or their nominated delegate, will provide a verbal explanation of the trial and the opportunity to ask questions and have these answered. This combined process of both written information and verbal exchange will constitute an overall process to facilitate participant/PR understanding of the information. It will also provide the best opportunity for the participant/PR understanding of the information to be demonstrated to the research member undertaking the opt-out approach. This brochure will detail the process for declining or opting out of study participation. They will be given the brochure to keep and may seek further information or opt-out at any time. The provision of the opt-out brochure will be documented in the participants medical record and a copy of the brochure will be placed in the participants medical records. If the participant or PR decides to opt-out of the trial this will be clearly documented in the medical record.

11.3.2 Consent for follow up using consent to continue approach

Subject to local HREC approval, and where opt-out consent is not consistent with local jurisdictional requirements and legislation, we will seek consent to continue participation in the trial for the purposes of follow up at 90 days and 12 months. The site PI, or their nominated delegate, will provide a plain language information sheet and consent form to the participant and/or PR at the earliest appropriate opportunity. The information sheet will explain all aspects of the trial and the opportunity to ask questions and have these answered. This combined process of both written information and verbal exchange will constitute an overall process to facilitate participant/PR understanding of the information. It will also provide the best opportunity for the participant/PR understanding of the information to be demonstrated to the research member undertaking the consent to continue. They will be given the information and consent form to keep and may seek further information or withdraw at any time. The consent process will be documented in the medical record and a copy of the information and consent form will be placed in the participant's medical record.

